7.1. Analysis Data Sets

7.1.1. Full Analysis Set (FAS)

Full Analysis Set is defined as all subjects who have received at least one dose of study medication. All safety and efficacy assessments will be analysed based on the analysis dataset.

7.1.2. Per Protocol (PP) Population

All FAS subjects who did not withdraw prior to completing 48 hours in the treatment period will be included in the Per Protocol (PP) population.

All primary and secondary efficacy endpoints will also be analyzed for the PP population.

7.2. Calculated Outcomes

The following are key endpoints derived from data captured at the sites via the EDC system. Complete documentation of the calculations and data manipulation required to go from the CRF database to the analysis database are contained in the companion documents – SDTM Programming Specification File (SDTM Spec) and ADaM Programming Specification File (ADaM Spec).

Outcome	Calculation	Comment
Study Day	= the days from Day 1 (Date of the First Study Infusion) to the event date	
Time in Trial (days)	= Study completion/withdrawal date – date of informed consent date + 1 day	
Time on Treatment	= Date of last infusion – Date of first infusion + 1	
Baseline value	= Value reported prior to the first study treatment	If multiple values collected prior to the first infusion, non-missing value closest to the date/time of the first infusion is considered as baseline value
Change from Baseline	= Value collected at time point (Visit) – Baseline value	
BMI	= $10000 * (\text{Weight in kg}) / (\text{Height in cm})^2$	Value will be rounded to keep one decimal point
Treatment Emergent Adverse Event (TEAE)	= No, if onset date/time AE is before the date/time of the first study infusion = Yes, otherwise	According to conservative rule, all AEs that cannot be determined as started before the first study infusion will be considered as TEAE

Outcome	Calculation	Comment
Time from baseline to achieving $\text{SpO}_2 \geq 94\%$ on room air	= Date of first achieving $\text{SpO}_2 \geq 94\%$ on room air – Date of first infusion + 1 = null if the subject did not achieve $\text{SpO}_2 \geq 94\%$ till study termination	
Number of ventilator-free days	= the number of days between Day 1 and Day 28 that subjects are both alive and free of mechanical ventilation	
Weaned from MV (Yes/No)	= Yes, if the subject was on MV and then weaned from MV through Day 28 = No, if the subject was on MV and kept using MV till Day 28 = null, if the subject did not use MV from Day 1 to Day 28	
Progressed to MV (Yes/No)	= Yes, if the subject progressed from non-invasive (at baseline) to MV on/before Day 28 = No, if the subject was keeping non-invasive till Day 28	
Time to Progression (TPP)	= First MV date – Date of first infusion + 1 = null, if the subject was keeping non-invasive till Day 28	
Time to hospital discharge	= Hospital discharge date – Study Day 1 + 1 = null if the subject was staying in hospital till Day 28	
Achieving 1-point OSCI Decrease at Visit (Yes/No)	= Yes, if OSCI at visit – OSCI at Day 28 (or End of Treatment) ≥ 1 = No, OSCI at visit – OSCI at Day 28 (or End of Treatment) < 1 = null, if OSCI at Day 1 and/or at visit were missing	
Time to Achieving 1-point OSCI decreasing	= Date of first achieving 1-point OSCI decreasing – Study Day 1 + 1 = null if never achieving 1-point decreasing	

Outcome	Calculation	Comment
Achieving 2-point OSCI Decrease at Visit (Yes/No)	= Yes, if OSCI at visit – OSCI at Day 28 (or End of Treatment) ≥ 2 = No, OSCI at visit – OSCI at Day 28 (or End of Treatment) < 2 = null, if OSCI at Day 1 and/or at visit were missing	
Time to Achieving 2-point OSCI decreasing	= Date of first achieving 2-point OSCI decreasing – Study Day 1 + 1 = null if never achieving 2-point decreasing	

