## **3. STUDY DESIGN**

The study is designed as a randomized double-blind study. All staff at the site will be blinded to the treatment allocation, including Pharmacy staff, and all Sponsor personnel will also be blinded. The randomization and allocation of kits will be managed by the data management group via an interactive web randomization system (IWRS).

### Part 1

Dose escalation will be randomized, double-blinded and placebo-controlled in 24 subjects (up to 48 if DLT occurs). Up to six subjects will receive either SOC plus USB002 (n=3) or SOC plus placebo (n=3) in up to 4 escalating doses.

COVID-19 diagnosed patients in pulmonary distress requiring supplemental oxygen will be eligible for enrollment once consent has been obtained from the subject or legal representative and eligibility has been confirmed. Screening assessments obtained prior to consent and within 72 hours of infusion start will be used to assess eligibility and will not require repeating, unless determined by the Investigator as needed.

Study registration (subject number assignment) will be conducted through the IWRS upon enrollment. The Investigator will confirm eligibility and notify the pharmacy so designated study pharmacy staff can request cohort assignment and a drug kit identification randomization number through IWRS system. The pharmacy will receive dosage instructions directly from the IWRS system.

Starting at Visit 1/0 hours, subjects will receive a continuous IV infusion of USB002 or

placebo for up to 96-hours. Safety will be assessed by changes in physical examination findings, changes in vitals and laboratory parameters. AEs will be collected from the time of informed consent; those occurring between informed consent and start of infusion will be designated as medical history, and those occurring after start of infusion will be designated as AEs. Baseline assessments are defined as those conducted on Visit 1, prior to start of infusion.

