### **3.1.5. Route of Administration**

USB002 or placebo will be administered by IV. The infusion rate of the reconstituted study medication/solution supplied by the pharmacist is fixed at 4.167 ml/hour (0.069 ml/min) for all dose levels and all subjects when a 100 ml infusion bag is used. The daily dose required for each subject is calculated and dispensed according to the instructions in the pharmacy manual.

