### **3.2. Dose Regimen and Escalation**

#### Part 1: Dose Escalation

During dose escalation, the study will follow a traditional “3+3” design with three subjects in each cohort receiving SOC plus USB002 and three subjects in each cohort receiving SOC plus placebo. Cohorts will be enrolled sequentially for USB002 dose, with subjects receiving active drug at four sequential cohort doses of 90, 300, 600 and 900 ug/kg/day.

DSMB escalation decisions will be conducted on unblinded data. In Part 1, data review to determine dose escalation, de-escalation and study stop will be conducted by the DSMB after the last subject in each cohort has completed infusion (96-hour timepoint). Recruitment will be halted during DSMB data review for dose escalation decisions. Notification of changes in dose concentrations (escalation or de-escalation) will be issued through the IWRS.

The first 6 subjects (3 SOC plus USB002 subjects and 3 SOC plus placebo subjects) will be treated at the lowest dose. If one subject experiences an AE that is determined by the DSMB to be a potential DLT, an additional 6 subjects (3 SOC plus USB002 and 3 SOC plus placebo) will be treated at the same cohort dose. If DLTs are experienced in the new cohort at the same dose, the study may be stopped, or dose de-escalated.

DLT of hypotension (systolic BP < 90 mmHg) is a possibility, which may require the administration of fluid boluses or IV pressor agents.

At the time of a DSMB safety review, if no DLTs are identified in the first cohort, approval will be issued to treat the next 6 subjects (3 SOC plus USB002 and 3 SOC plus placebo) at the next dose. The DSMB safety reviews will be repeated between cohorts until the MTD or top dose of 900  $\mu$ g/kg/day is reached.

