### **3.4 Treatment Period**

#### Part 1

Treatment will start during Visit 1/hour 0 and continue for up to 96 hours.

#### Part 2

MTD treatment will start at Day 1 and continue for up to 14 days.

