#### **7.2.2. Extent of Exposure**

A summary of exposure to study drug including the total exposure to USB002 and the duration of exposure, will be provided.

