8.1.1. Patient Disposition

All subjects will be accounted for. All early withdrawals will be summarized by primary reason for discontinuation; these will be summarized by treatment group.

Treatment exposure (time in trial and time on treatment) will be summarized by cohort for all subjects in the analysis dataset.

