8.1.4. USB002 Administration

USB002 administration data, including dose of administration, infusion start/end date, start/end time, start rate of infusion, and all information of infusion rate changes, infusion incompletion reason, and related AEs, if applicable, will be listed.

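### SAP 7.2 measures Time on Treatment in undefined calendar-date units for a continuous infusion of at most 96 hours, and the total-exposure summary promised in the protocol is missing without being declared.

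*SAP*

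**What the plan says.** Protocol 3.4 sets the Part 1 treatment period: "Treatment will start during Visit 1/hour 0 and continue for up to 96 hours". Protocol section 3 describes this as a continuous IV infusion. Protocol 3.1.5 gives the infusion rate as "fixed at 4.167 ml/hour (0.069 ml/min) for all dose levels and all subjects when a 100 ml infusion bag is used". Doses are daily rates, with "subjects receiving active drug at four sequential cohort doses of 90, 300, 600 and 900 ug/kg/day" (protocol 3.2), so the amount a subject receives depends on the hours infused.

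Protocol 7.2.2 commits to an exposure summary "including the total exposure to USB002 and the duration of exposure".

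The SAP treats exposure in three places:

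- Section 7.2 computes Time on Treatment as "Date of last infusion – Date of first infusion + 1", with no unit and an empty comment cell.
- Section 8.1.1 says "Treatment exposure (time in trial and time on treatment) will be summarized by cohort". It mentions no amount of drug.
- Section 8.1.4 lists the administration data, among them "infusion start/end date, start/end time, start rate of infusion, and all information of infusion rate changes", together with reasons for incomplete infusion and related AEs.

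SAP section 6 declares three changes from the protocol: no Part 2 analyses, no time-to-event estimates for OSCI, and no analysis of vasoactive use. Total exposure is not among them.

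**The concern.** Counting dates inclusively suits a drug given once a day. For a continuous infusion limited to 96 hours it counts the calendar days touched, so the result depends on the clock time at which the infusion began. The duration rule is also ambiguous. The SAP uses the singular idea of a first and a last infusion for what the protocol treats as one infusion, delivered from successive bags.

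Safety and tolerability by dose are the primary endpoint. The exposure table is where a reader looks to see how much drug each cohort received. Enrolment stopped at 21 subjects, six in each of the first three cohorts and three in the fourth, so one shortened infusion is a visible share of any cohort. A table that gives an inflated and coarse duration, and no amount of drug, serves that purpose poorly.

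**Working it through.** The documents state no figure on this point, so there is none to reproduce. The check applies the SAP rule to infusions of known length.

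**Inputs.** Maximum duration 96 h = 4.0 days (protocol 3.4). Bag volume 100 mL at 4.167 mL/h (protocol 3.1.5), so one bag lasts 100 / 4.167 = 24.0 h and 96 h takes four bags. Daily doses 90, 300, 600 and 900 ug/kg (protocol 3.2).

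**Reading A: the last date is the infusion end date.** The formula equals the number of midnights crossed plus 1. For an infusion of h hours with a start time spread evenly over the day, the expected number of midnights is h/24. The expected value is therefore h/24 + 1, an average excess of exactly one day at any duration. Applying the rule to all 1,440 start minutes of a day gives:

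| Infusion | Elapsed days | SAP value |
|---|---|---|
| 12 h | 0.5 | 1 for half of start times, 2 for the other half |
| 24 h | 1.0 | 2 always |
| 48 h | 2.0 | 3 always |
| 72 h | 3.0 | 4 always |
| 84 h | 3.5 | 4 for half, 5 for half |
| 96 h | 4.0 | 5 always |

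The relative excess is 1/4 = 25% at 96 h, 1/2 = 50% at 48 h and 1/1 = 100% at 24 h.

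The durations that can produce each value, up to the 96 h limit, are:

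- 1: under 24 h
- 2: any duration under 48 h
- 3: over 24 h and under 72 h
- 4: over 48 h and under 96 h
- 5: over 72 h, up to 96 h

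A value of 2, 3 or 4 thus spans almost 48 h. A value of 3 does not show whether 48 hours were completed.

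**Reading B: the last date is the start date of the last 24-hour bag.** With bags run back to back, the formula rounds the duration up to whole 24 h periods: 24 h reads 1, 48 h reads 2, 72 h reads 3 and 96 h reads 4. These match elapsed time at exact multiples of 24 h, but 73 h, 84 h and 95 h all read 4 as well.

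**Amount of drug.** For an uninterrupted 96 h, daily dose × 4 gives 90 × 4 = 360, 300 × 4 = 1,200, 600 × 4 = 2,400 and 900 × 4 = 3,600 ug/kg. The SAP plans no such product. A reader who multiplied the daily dose by a reported 5 days would get 450, 1,500, 3,000 and 4,500 ug/kg, each 25% too high.

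**Promise against plan.** Protocol 7.2.2 names two quantities, total exposure and duration. SAP 8.1.1 names time in trial and time on treatment, both of which are durations. No section of the SAP summarises an amount, and section 6 is silent on it.

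**The case against.** The best defence is that last minus first plus 1 is a recognised convention for days on which treatment was given, and the same SAP table uses it for time in trial, time to discharge and time to progression. A 96-hour infusion begun at noon does fall on five calendar dates. This stands as far as it goes: the formula is not an arithmetic mistake. But the row gives no unit, and the same table uses date and time for the TEAE flag and the baseline value, so finer timing was available.

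It can also be said that reading B gives 4 and 1, which agree with elapsed time. That is correct, and it means that 5 and 2 are conditional on reading A. The two readings differ by a full day at 24, 48, 72 and 96 h, which is itself a reason to define the term.

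Three stronger readings are tempting, and the documents do not support them:

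- *Exposure is the denominator of the safety results.* It is not. SAP 8.2.1 and protocol 7.2.3.1 report counts and percentages of events and subjects, and SAP 7.4 makes no inference.
- *The rule hides poor tolerability.* SAP 8.1.4 lists start and end times, rate changes, reasons for incompletion and related AEs, and SAP 8.1.1 summarises early withdrawals by reason. With 21 subjects, a listing shows every early stop. A short infusion need not mean intolerance either, because the protocol also ends infusion when the oxygen-saturation criterion is met.
- *Early stoppers are overstated most.* This is true only as a ratio. The average excess is one day throughout, so absolute differences between subjects or cohorts are unchanged on average.

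Nor does any decision rest on the variable. The per-protocol set is defined in hours in its own right (SAP 7.1.2), and escalation rests on DSMB review of the EDC data.

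Finally, the protocol does not define total exposure as cumulative dose, and the SDTM and ADaM specifications cited in SAP 7.2 are not available and might hold a finer derivation. Both caveats stand. But total exposure is named alongside duration, so it must mean something else, and amount of drug is the natural reading. The conclusion concerns the SAP text only.

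**Conclusion.** The point holds as a modest one, in two parts. First, Time on Treatment is not adequately defined for a continuous infusion. Under the end-date reading, which is the natural one for a single infusion recorded with start and end dates, it exceeds elapsed time by one day on average (5 against 4.0 for a full infusion) and cannot separate durations within a span of almost 48 h. Under the bag-start reading the excess disappears at whole multiples of 24 h, but the value is still coarse. The figures assume an uninterrupted infusion, an evenly spread start time for the average and, for the second reading, back-to-back 24-hour bags.

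Second, the SAP text omits the total-exposure summary in protocol 7.2.2 and does not declare the omission. This part does not depend on how the last infusion is dated.

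The consequence is limited to one descriptive exposure table, supported by full listings. No test, event rate or analysis set is affected. It is still worth correcting, because exposure by dose is basic reporting in a dose-escalation safety study.

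**What to change.** In SAP 7.2, define Time on Treatment in hours: infusion end date/time minus infusion start date/time, less documented interruptions. Summarise it by cohort in section 8.1.1.

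In the same section, add total USB002 received (ug/kg) and percent of the planned 96-hour amount, by cohort. Where the 100 mL bag and fixed rate apply, with assigned daily dose D and recorded rate r (mL/h) over each interval of t hours:

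- total received = D × Σ (r / 4.167) × (t / 24)
- percent of planned = 100 × Σ (r / 4.167) × t / 96

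An uninterrupted 96 h at the fixed rate returns 4 × D and 100%. This assumes that pauses are recorded as rate changes or separate start and stop times; the data specification should confirm it.

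If the sponsor prefers not to summarise total exposure, declare and justify the omission in SAP section 6.

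The cost is a few lines of SAP text and a short derivation from times and rates that SAP 8.1.4 already lists. No new data are needed.

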#### 2.1.1 Primary Objectives and Endpoints

The primary objectives of safety and tolerability of USB002 will be evaluated for rate of occurrence and severity of AEs resulting from clinical changes (Visit 1/Day 1 to Day 28): cardiovascular parameters, to include blood pressure (BP), heart rate (HR), 12-lead electrocardiogram (ECG), and requirements for inotropes and vasopressors; laboratory parameters, to include kidney and liver function.

The primary endpoint of preliminary efficacy will be demonstrating the difference between USB002 and placebo groups in time to peripheral capillary oxygen saturation ( $\text{SpO}_2$ )  $\geq 94\%$ , sustained for at least 48 hours, on room air through Day 28.

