### 5.3 Other Assays or Procedures

Other assays or procedures include:

- Pregnancy test (for females of childbearing potential).
- OSCI (Appendix 1);
  - In addition to study required OSCI status collection, any additional OSCI assessments conducted during the study will also be collected.
- SBT (Appendix 2);
- Chest X-ray (required at screening only);

- 12-lead ECG to include HR and QRS intervals, QT/QTcF/QTcB; Correlation of QT values using Fridericia's formula;
- Vitals to be captured daily; and during the infusion period at a minimum of every 8 hours. Vitals to include systolic and diastolic BP, HR, RR and temperature;
  - If BP changes significantly post start of infusion, mean arterial pressure will be collected at 15-minute intervals, until resolution;
- Weight measured at screening only;
- Study-required respiratory assessments (first and last assessments can be based on 24 hour clock or from infusion time):
  - Arterial Blood Gas (ABG): If multiple assessments are conducted daily, the first and last assessment of the day will be collected; missed ABGs do not qualify as deviations,
  - $\text{FiO}_2$  (%) – The highest value in a 24-hour period to be recorded in the event of multiple daily assessments,
  - $\text{PaO}_2/\text{FiO}_2$  ratio, the  $\text{PaO}_2$  value to be obtained from the ABG when performed,
  - Respiratory rate (breaths/min) – The highest value in a 24-hour period to be recorded in the event of multiple daily assessments,
  - $\text{SpO}_2$  (%) – The lowest value in a 24-hour period to be recorded in the event of multiple daily assessments.

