#### **Days 7, 9, 12 and 14**

- Laboratory (chemistry, hematology and coagulation per Section 5.2) (Day 14);
- 12 lead-ECG (Days 7, 9, 14);
- Vitals;
- Respiratory assessments per Section 5.3;
- SBT at Days 7, 9 and 14 and at any time that weaning criteria is met;
- AEs;
- Concomitant medications.

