## 7.2 Description of Statistical Methods

### 7.2.1 Analysis of the Efficacy Endpoint(s)

Efficacy assessments will be based on the safety analysis set, which is defined as all subjects who have received at least one dose of study medication. Data relating to efficacy response will be listed and summarized by treatment group and time point, as appropriate. Any efficacy related outcomes in Part 1 will be present descriptively and will be detailed in the SAP.

Summary statistics (mean, median, standard deviation, minimum, and maximum) and change from baseline to each scheduled study assessment for ventilator readings will be presented by treatment group. Baseline is defined as the latest non-missing assessment prior to the first study drug infusion.

The primary efficacy outcome, time to peripheral capillary oxygen saturation ( $\text{SpO}_2$ )  $\geq 94\%$  on room air, sustained for at least 48 hours, through Day 28, will be estimated and compared between the two treatment groups using Kaplan-Meier (KM) analysis. Subjects who do not achieve  $\text{SpO}_2 \geq 94\%$ , sustained for at least 48 hours, or die by Day 28 will be censored at Day 28. As a supplemental analysis, an analysis using a Cox proportional hazards model incorporating the baseline covariates: age, baseline severity, and comorbidity, will be performed.

The secondary efficacy outcome of proportion of subjects with all-cause mortality within 60 days from start of treatment, will be compared between the two treatment groups using Fisher's exact test. In addition, as a supplemental analysis, a logistic regression analysis will also be performed to adjust for the same baseline covariates in the primary efficacy outcome analysis: age, baseline severity, and comorbidity.

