Respiratory distress in untreated COVID-19 infected patients presents as a progressive continuum from SOB to cardiopulmonary collapse and death. It is diagnosed in symptomatic patients with bilateral lung infiltrates with confirmed positive tests for COVID-19. Without supportive therapy, pulmonary distress rapidly progresses to hospitalization where supplemental oxygen can be given by nasal cannula, high-flow mask, BiPAP mask, and eventually intubation and assisted ventilation. Overall, the physiological damage to cells and structures of the lung can begin within hours of exposure and progress within days (Fahy 2012). The pathologic hallmarks of COVID-19-induced pulmonary distress include neutrophilic alveolitis, hyaline membrane disease secondary to protein transudation and precipitation in the airspace, microthrombi secondary to the generation of procoagulant mediators as well as endothelial and epithelial injury. For these reasons, there is considerable interest in the use of an Angiotensin 1-7 [A(1-7)] to treat patients who have developed respiratory distress from COVID-19 infection (Soto 2020, Piero 2020, NCT 04332666).

This study's investigational product USB002 is pharmaceutically formulated A(1-7), a non-hypertensive derivative of Angiotensin-II (A-II) and is suspended in a vehicle as a sterile solution of USB002 (22.5 mg/ml) which is stable at room temperature for 90 days.

According to the protocol (see Section 4.1 Study Design), this clinical trial includes two parts (dose escalation phase and dose expansion phase). Due to enrolment difficulty to find subjects meeting the study eligibility criteria, in Dec. 2022, the sponsor decided to stop the enrollment and terminate the trial early, when 21 subjects (all Part 1) have been enrolled: 6 subjects in each of the first three cohorts (90, 300 and 600 ug/kg/day) and 3 subjects in Cohort 4, (900 ug/kg/day).

3. Objectives

The objectives of the study are twofold:

- To determine the safety and tolerability of USB002 in treatment of respiratory distress from COVID-19 infection; and
- To identify an early efficacy signal of USB002.

Part 1:

- To determine the maximum tolerated dose (MTD) of USB002 (up to 900 ug/kg/day).

Part 2:

- To determine preliminary efficacy of the USB002 MTD following up to 14 days of continuous infusion.

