4.2. Primary Endpoints

The primary endpoint of the study will be safety and tolerability, as demonstrated by adverse events (AE), changes in laboratory assessments, ECG assessments, vital signs, and concomitant medications (inotropes and vasopressors).

The primary endpoint of preliminary efficacy will be demonstrating the difference between USB002 and placebo groups in time to peripheral capillary oxygen saturation (SpO_2) $\geq 94\%$ on room air, sustained for at least 48 hours, through Day 28.

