8.2.6. Time to peripheral capillary oxygen saturation (SpO_2) $\geq 94\%$ on room air

The time from baseline to achieving $\text{SpO}_2 \geq 94\%$ on room air will be calculated for each subject. Two summaries will be provided:

- All subjects treated with USB002 vs. all placebo subjects
- USB002 subjects vs. placebo subjects by cohort. That is, comparing between two treatment groups within each cohort (dose level)

All data will be listed.

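### The SAP computes the co-primary SpO2 outcome from the first qualifying date and omits the 48-hour condition in the endpoint's definition, without declaring a change

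*SAP*

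**What the plan says.** Protocol 2.1.1 sets the efficacy endpoint as the time to SpO2 of 94% or more, "sustained for at least 48 hours, on room air through Day 28". Protocol 7.2.1 repeats the 48-hour condition, both for the event and for deciding who is censored at Day 28. For Part 1 it then hands over to the SAP: "Any efficacy related outcomes in Part 1 will be present descriptively and will be detailed in the SAP".

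SAP 4.2 keeps the definition, "on room air, sustained for at least 48 hours, through Day 28". SAP 8.2 states it again and calls the endpoint co-primary.

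The two SAP places that say what will be computed differ:

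- SAP 7.2, Calculated Outcomes: "Date of first achieving $\text{SpO}_2 \geq 94\%$ on room air – Date of first infusion + 1". The value is null only if the subject never reached the threshold before the study ended.
- SAP 8.2.6: heading and text describe time to SpO2 of 94% or more on room air, with no duration. The result is summarised for all USB002 against all placebo subjects, and again by cohort, "comparing between two treatment groups within each cohort (dose level").

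SAP Section 6 declares three changes: Part 2 is not analysed, the OSCI time-to-event analysis becomes descriptive, and the vasoactive-agent endpoints are dropped. The SpO2 definition is not among them.

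**The concern.** The endpoint as defined is a sustained recovery. The derivation as written is a first touch of the threshold. A subject who has one qualifying recorded day and then goes back on oxygen is not an achiever under the definition, but receives a time under SAP 7.2. A subject who relapses and later recovers for good receives a time that is too early. The summary would be presented as the co-primary outcome of SAP 8.2 while measuring something else.

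Because Part 1 is the only part that enrolled, and the protocol leaves its efficacy detail to the SAP, the SAP derivation is what a programmer would follow. A reader who compares the report with the protocol would find no declared change to explain the difference.

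**Working it through.** **1. Definitions side by side**

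| Place | 48-hour condition | Upper limit |
|---|---|---|
| Protocol synopsis, 2.1.1, 7.2.1 | yes | Day 28 |
| SAP 4.2 | yes | Day 28 |
| SAP 8.2 | yes | Day 28 |
| SAP 7.2 derivation and its null rule | no | end of study |
| SAP 8.2.6 heading and text | no | none stated |
| SAP Section 6 | not mentioned | not mentioned |

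SAP 8.2 also points to a Section 8.2.7 for this outcome. The outcome is in 8.2.6, and 8.3 follows it.

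**2. Direction within a subject.** Any 48-hour run contains a qualifying value, so the first-date rule can never give a later time or fewer achievers than the sustained rule. The effect on the difference between arms depends on which arm the affected subjects are in, and the documents do not show this.

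**3. What the recorded data allow.** For SpO2, Protocol 5.3 keeps "The lowest value in a 24-hour period to be recorded in the event of multiple daily assessments". A brief spike within a day would therefore not normally count. One isolated qualifying day still would.

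**4. Effect of one subject.** SAP Section 2 gives the enrolment: "6 subjects in each of the first three cohorts (90, 300 and 600 ug/kg/day) and 3 subjects in Cohort 4". Cohorts 1 to 3 have 3 per arm by design. The split in Cohort 4 is not stated, so a pooled arm has 9 + 0 = 9 to 9 + 3 = 12 subjects, assuming that all enrolled subjects were dosed.

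- Cohort arm: 1/3 = 33.3 points.
- Pooled arm: 1/12 = 8.3 to 1/9 = 11.1 points.

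**5. Effect on time (assumed days).** Take an isolated qualifying day on Day 3 and a sustained run from Day 9, in an arm of three achievers.

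- SAP 7.2 gives 3.
- If the event date is the start of the 48 hours, the time is 9. The difference is 6 days, and the arm mean moves by 6/3 = 2.0 days.
- If it is the completion, the time is 11. The difference is 8 days, and the arm mean moves by 8/3 = 2.7 days.
- Run starting Day 7: (7 − 3)/3 = 1.3 to (9 − 3)/3 = 2.0 days.
- Run starting Day 14: (14 − 3)/3 = 3.7 to (16 − 3)/3 = 4.3 days.

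**6. How often it could happen.** The documents give no relapse rate. As an illustration only, let each day qualify independently with probability p. The shares meeting the rule by Day 28 on one day, two consecutive days and three consecutive days are:

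- p = 0.3: 100%, 87.4% and 41.4%
- p = 0.7: 100%, 100% and 99.8%

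Serial readings in one patient are not independent, so these figures show only that the gap can run from negligible to large.

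**The case against.** The strongest reply is that SAP 7.2 is shorthand. The full definition stands in 4.2 and in 8.2, which is the parent section of 8.2.6. SAP 7.2 refers to SDTM and ADaM specifications for the complete calculations, and these are not available here. The same table also shortens the ventilator-free-days and weaning definitions, dropping the 48 hours after extubation that SAP 4.3 requires. This looks like abbreviation more than a deliberate redefinition.

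That may well be the intent, but it does not repair the text. The derivation says first, and its null rule drops both the 48 hours and Day 28. If the companion specifications carry the condition, they contradict 7.2. If they do not, they contradict 4.2 and 8.2. Even on the shorthand reading, nothing says whether the event is the start or the completion of the 48 hours.

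Several points on consequence do stand. The trial stopped after 21 Part 1 subjects, no inference is made, and no alpha, power or dose decision rests on this outcome. All SpO2 results to Day 28 will be listed, so a reader could re-derive the endpoint. SAP 8.2 already limits those listings to Day 28, so correcting the end-of-study wording may change little in practice. The SAP specifies a time, not an achiever proportion, so the proportions above are read from who has a non-null time. The one-subject figures are simple 1/n arithmetic and do not show that any subject is affected.

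**Conclusion.** The concern holds. The SAP text that governs computation of the co-primary efficacy outcome contradicts the SAP's own definition and the protocol's, and the difference is undeclared. It should be fixed.

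The size per affected subject is 33 points in a three-subject cohort arm or 8 to 11 points in a pooled arm. For a relapsing subject who later recovers, the mean of a three-achiever arm moves by about 1.3 to 4.3 days under the assumed timings. The number of affected subjects and the direction of any change in the group difference are unknown. The harm is confined to descriptive reporting.

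**What to change.** In SAP 7.2 and 8.2.6:

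- Add the 48-hour condition on room air and end the window at Day 28.
- State whether the event date is the start or the completion of the 48 hours.
- State how the 48 hours is confirmed when recorded values are days apart. One option is consecutive recorded room-air values of 94% or more, spanning at least 48 hours, with no oxygen use recorded between them.
- Show separately the subjects who cannot be confirmed, such as those discharged first.
- Correct the cross-reference in SAP 8.2.

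If the first-date version is kept, declare it in Section 6 and label it supportive.

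The cost is a text change, a confirmation rule and the matching ADaM specification, with no new data collection. The drawback is that some subjects will be unconfirmable. In the Part 1 visit text of Protocol 5.4.2, respiratory assessments after Visit 5 fall on "Days 7, 9, 12 and 14", then Day 16. Counting from Day 5, the gaps are 2, 2, 3, 2 and 2 days. None is listed for Days 18 to 28, so a value first qualifying on Day 16 has no later scheduled value to confirm it.
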